1.1. Study Schema

Figure 1: Treatment Algorithm

Abbreviations: BM=bone marrow aspirate; CR=complete remission; CRi=complete remission with incomplete hematologic recovery; HCT=hematopoietic cell transplant

Notes: The postinduction bone marrow aspirate will be collected on approximately Day 14 to 21.

Participants with a FLT3 mutation may also receive treatment with midostaurin on Days 8 through 21 at the investigator's discretion and dependent on local availability. For these participants, the postinduction bone marrow aspirate will be collected on Day 22 or 23.

Refer to Table 7 for all criteria required to achieve a CR or CRi.

1.2. Schedule of Activities

Table 1: Schedule of Activities/Assessments: Induction Cycle and Reinduction Cycle (as applicable)

Study Day:	Screen ^a	BL/ D1	D 2	D 3	D 4	D 5	D 6	D 7	D 8	D 14- 21	D22 until count recovery or Day 42 ^c	Post-CR	Early Therapy DC	Notes
Examination / Procedure														Study day is relative to start of each treatment cycle
Informed consent	X													
Eligibility criteria	X	X												
Demographics	X													
Medical history	X	X												
ECOG status (induction only)	X	X												
Physical exam and vital signs	X													Predose findings=medical history; Findings after first dose=AE
Height / Weight	X													
ECG (induction only)	X	X							X					D1: Before and after bolus dose; D8: At the end of infusion
Echocardiogram / MUGA scan	X													Repeat per standard of care.
Pregnancy test (as applicable)		X												Women of childbearing potential
Peripheral blood samples:														
– Molecular genetics (central)	X													
– Immunophenotyping (central)	X													
– FISH (central)	X													
– Fibrinogen, D-dimer (local)	X													
– Clinical chemistry (local)	X	X	X		X		X		X	D14				
– Hematology (local)	X	X	X		X		X		X	X	X			Every other day through recovery.
– PT/INR, aPTTe,f (local)	X	X ^f	X	X	X	X	X	X	X	D14				Do not draw from the same line used for drug administration ^e
– PK blood samples ^e (central) (induction only) (at sites with appropriate capabilities)		X			X				X					(±10min) D1: predose, end of bolus, and 1 and 12 hours after bolus; D4: morning; D8: end of infusion, and 0.5, 1, 2, and 4 hours after end of infusion
– HMGB1 ^{e,g} (central)		X			X				X	D14	At recovery ^{b,c}			
– Biobanking (central)	X										X ^c			Optional, per local regulation/approval

Consolidation Therapy, as applicable – see Table 2

Study Day:	Screen ^a	BL/ D1	D 2	D 3	D 4	D 5	D 6	D 7	D 8	D 14- 21	D22 until count recovery or Day 42 ^c	Post-CR	Early Therapy DC	Notes
Examination / Procedure													Study day is relative to start of each treatment cycle	
Bone marrow aspirate/ biopsy:														
– MRD analyses (central)	X										At recovery ^{b,c}			Required. Use first draw of marrow.
– Biobanking (central)	X										At recovery ^{b,c}			Optional, per local regulation/approval
– Morphology (local)	X									X ^b	At recovery ^{b,c}			
– Cytogenetics (local)	X													
Buccal swab or saliva specimen (central) (induction only)											X			Optional, single sample for germ line analysis
Randomization ^a		X												
Cytarabine – continuous infusion		X	X	X	X	X	X ^d	X ^d						100 mg/m ² /day (Note: FLT3-positive participants may receive 200 mg/m ² /day)
Idarubicin 12 mg/m ² /day OR Daunorubicin 60 mg/m ² /day		X	X	X ^d										
Study intervention – bolus		X												4 mg/kg via IV push, begin 30 min after anthracycline infusion ends
Study intervention – continuous infusion		X	X	X	X	X	X ^d	X ^d						0.25 mg/kg/hour; Begin after bolus dose
Adverse event assessments	Procedure-related SAEs	All AEs ----- →										X	Record through 42 days after start of the last induction or consolidation treatment cycle (regardless of completion or discontinuation)	
Concomitant medications	X	----- →										X		
Medical resource utilization		----- →										X		

Abbreviations: AE=adverse event; aPTT=activated partial thromboplastin time; CR=complete response; D=day; D14=Day 14 (only day specified within window); DC=discontinuation; ECG=electrocardiogram; ECOG=Eastern Cooperative Oncology Group; FISH=fluorescence in situ hybridization; HMGB1=high mobility group box protein 1; MRD=measurable residual disease; MUGA=multigated acquisition scan; PK=pharmacokinetics; PT/INR=prothrombin time/international normalized ratio; SAE=serious adverse event

Refer to footnotes on the next page

^a All prestudy/screening procedures (including cytogenetic and molecular analyses) will ideally be completed within 14 days of randomization. First dose of study intervention should be administered as soon as possible after randomization, and must be administered no more than 24 hours after randomization. Screening procedures do not need to be repeated prior to reinduction.

^b Bone marrow aspirate/biopsy will be performed once between approximately Day 14 and Day 21 (Day 22-23 for participants taking midostaurin), when peripheral blood is negative for persistent AML, to determine the need for reinduction. (If the ~Day 14 bone marrow is not evaluable or assessment of aplasia is equivocal, a repeat evaluation may be performed 5 to 14 days later, at the discretion of the investigator, in order to determine effect and need for second induction). Thereafter, additional bone marrow samples will be collected to confirm response/persistence/relapse after second induction and consolidation cycles. For participants who achieve CR/CRi, measurable residual disease assays will be performed by the central laboratory on the recovery marrow sample.

^c Count recovery is defined as an absolute neutrophil count >1000/ μ L and a platelet count >100,000/ μ L. If count recovery occurs, perform bone marrow aspirate/biopsy within 7 days. If count recovery has not occurred by ~Day 36 after induction or reinduction, perform a bone marrow aspirate/biopsy on or before Day 42 to evaluate disease status.

^d Participants who do not achieve leukemia-free state (<5% bone marrow blasts) on bone marrow aspirate performed between ~Days 14-21 (Day 22-23 for participants taking midostaurin) may receive a reinduction cycle. Participants 18 to 59 years will receive the same 7+3 regimen; participants \geq 60 years will receive a modified “5+2” regimen, with cytarabine and study intervention administered on Days 1 through 5 and idarubicin/daunorubicin on Days 1 and 2.

^e Do not draw blood (especially for aPTT or PK analyses) from the same line that is used for study intervention administration. Drawing blood from a heparinized line may falsely alter results obtained; if using an indwelling catheter, draw ~5 mL of blood from the line for discard before drawing the aPTT and PK samples.

^f Draw blood for aPTT measurements no sooner than 8 hours after the bolus dose. During the continuous infusion, measure aPTT daily.

^g Refer to laboratory manual for instructions on obtaining a separate sample for HMGB1 analyses versus using a biobanked sample.

Note: All participants will be followed-up for long-term outcomes for 5 years after randomization. See Section [8.2.3](#).

Table 2: Schedule of Activities/Assessments: Consolidation Cycles

Study Day: Examination / Procedure	D1	D2	D3	D4	D5	D6	D14	D7 until count recovery or D42 ^h	Follow-up	Notes
Weight	X									Day is relative to start of each treatment cycle
Bone marrow aspirate/ biopsy:										After each consolidation cycle and to confirm response/ relapse/ persistent disease
–Morphology (local)								X – at recovery		
–MRD analyses (central)								X – at recovery		After each consolidation cycle
–Biobanking (central)								X – at recovery		Optional, per local regulations/approvals
Peripheral blood samples:										
–Hematology (local)	X	X		X		X	X	X		Every other day through recovery
–Clinical chemistry (local)	X	X		X		X	X			
–PT/INR, aPTT ^{i,j} (local)	X	X	X	X	X	X	X			
–HMGB1 ^{g,i} (central)	X							X – at recovery		
–Biobanking (central)								X – at recovery		
Cytarabine – Infusion over 3 hours, twice daily	X		X		X					18 to 59 years: 3 g/m ² /dose; ≥60 years: 1.5 g/m ² /dose
Study intervention – bolus	X									4 mg/kg via IV push over 5 minutes, begin 30 minutes after cytarabine infusion ends
Study intervention – continuous infusion	X	X	X	X	X					0.25 mg/kg/hour. Begin after bolus dose
Adverse event assessments								→		
Concomitant medications								→		Record through 42 days after the start of last cycle (regardless of completion or discontinuation)
Medical resource utilization								→		

Abbreviations: aPTT=activated partial thromboplastin time; CR=complete response; D=day; HMGB1=high mobility group box protein 1; MRD=measurable residual disease; PT/INR=prothrombin time/international normalized ratio

^g Refer to laboratory manual for instructions on obtaining a separate sample for HMGB1 analyses versus using a biobanked sample. Only samples from the last consolidation cycle will be analyzed.

^h Count recovery is defined as an absolute neutrophil count >1000/µL and a platelet count >100,000/µL.

If count recovery has not occurred by ~Day 36, perform a bone marrow aspirate/biopsy on or before Day 42 to evaluate disease status.

ⁱ Do not draw blood (especially for aPTT analyses) from the same line that is used for study intervention administration. Drawing blood from a heparinized line may falsely alter results obtained; therefore, if using an indwelling catheter, draw approximately 5 mL of blood from the line for discard before drawing the sample for analysis.

^j Draw blood for aPTT measurements no sooner than 8 hours after the bolus dose. During the continuous infusion, measure aPTT daily.

^k All participants will be followed-up for long-term outcomes for 5 years after randomization. See Section 8.2.3.

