3. OBJECTIVES AND ENDPOINTS

For definitions and response and outcomes criteria, refer to Section 8.2.2 and [Appendix 7](#).

Objectives	Endpoints
Primary Efficacy	

 To compare the efficacy of dociparstat plus standard chemotherapy versus standard chemotherapy alone as upfront treatment for newly-diagnosed AML 	
 Overall survival (OS).
Key Secondary Efficacy	

 To compare the efficacy of dociparstat plus chemotherapy versus chemotherapy alone with respect to event-free survival (EFS). 	
 EFS following CR. Defined as time from randomization to treatment failure, relapse, or death from any cause, whichever occurs first, with treatment failure defined as failure to achieve CR within 42 days of the start of induction (or start of reinduction, when applicable).
Secondary Efficacy	

 To compare the efficacy of dociparstat plus chemotherapy versus chemotherapy alone with respect to event- and relapse-free survival. 	
 EFS following CR/CRI, with treatment failure defined as failure to achieve CR/CRI within 42 days of the start of induction (or start of reinduction, when applicable). Relapse-free survival (RFS) after CR. RFS after CR/CRI.

 To compare MRD status with dociparstat plus chemotherapy versus chemotherapy alone. 	
 Proportion of participants who achieve CR with MRD_{neg}, as determined by multiparameter (multicolor) flow cytometry (MFC), at the end of induction and consolidation therapy. Proportion of participants who achieve CR/CRI with MRD_{neg}, as determined by MFC, at the end of induction and consolidation therapy. Proportion of participants who achieve MRD_{neg} (regardless of CR), as determined by MFC, at the end of induction and consolidation therapy. Association between CR with MRD_{neg} and relapse. Association between MRD_{neg} and relapse. Association between MRD_{neg} and OS.

 To compare post-induction response rates after treatment with dociparstat plus chemotherapy versus chemotherapy alone. 	
 Proportion of participants who achieve CR. Proportion of participants who achieve CR/CRI. Proportion of participants who achieve CR or complete remission with partial hematologic recovery (CRh).

Objectives	Endpoints

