8.2.2. Response Criteria and Outcome Measures

Response criteria and outcome measures (Table 7) are based on definitions from ELN (Döhner 2017).

Table 7: Response Criteria and Outcomes Measures

Response / Outcome	Definition
Response	Complete remission with complete hematologic recovery (CR) Defined for all study participants at the end of induction therapy. Bone marrow blasts <5%, absence of circulating blasts and blasts with Auer rods, absence of extramedullary disease, ANC >1.0 x 10 ⁹ /L (1000/µL), and platelet count >100 x 10 ⁹ /L (100,000/µL). Recovery of ANC and platelet counts within 7 days before or 7 days after bone marrow biopsy showing blasts <5% may be used to assess best response.
	CR with incomplete hematologic recovery (CRI) Defined for all study participants at the end of induction therapy. All CR criteria (bone marrow blasts <5%; absence of circulating blasts and blasts with Auer rods; absence of extramedullary disease), except for residual neutropenia ($\leq 1.0 \times 10^9/L$ [1000/µL]) or residual thrombocytopenia ($\leq 100 \times 10^9/L$ [100,000/µL]). [Note: Participants with both residual neutropenia and residual thrombocytopenia are not considered to have achieved CRI.]
	CR with partial hematologic recovery (CRh) Defined for all study participants at the end of induction therapy. CR criteria (bone marrow blasts <5%; absence of circulating blasts and blasts with Auer rods; absence of extramedullary disease), with partial recovery of peripheral blood counts (ANC >0.5 x 10 ⁹ /L [500/µL] and partial recovery of platelets >50 x 10 ⁹ /L [50,000/µL], but the count recovery criteria for CR are not met).

Response / Outcome	Definition
Measurable residual disease negative (MRD _{neg})	
Defined for all study participants at the end of induction and consolidation therapy.
 
Negative (undetectable) MRD in recovery (~Day 22-42) bone marrow, as measured by MFC (0.1% detection limit).

Failure (induction failure)	Failure to achieve CR (or CR/CRi) within 42 days of the start of induction therapy (or start of reinduction therapy when applicable).
Relapse (hematologic)	
Defined through 5 years after randomization only for participants achieving CR (or CR/CRi) during induction/reinduction.
 
After achievement of CR/CRi, bone marrow blasts $\geq 5\%$, reappearance of blasts in the blood, or development of extramedullary disease.

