8.9. Biomarkers

- For all participants, bone marrow aspirate/biopsy samples will be collected and tested for MRD via MFC at screening and after hematologic recovery for each cycle of induction and consolidation chemotherapy (as specified in the Schedule of Activities) to evaluate the association with dociparstat treatment and the observed OS and EFS.
- Blood samples will be collected during induction and consolidation therapy to measure plasma levels of HMGB1, which is expressed in tumor tissues and higher levels have been correlated with worse clinical prognosis. The association of dociparstat with lower HMGB1 levels will be evaluated. See Section 1.2 for collection timepoints. For participants who receive multiple consolidation cycles, only samples from the last consolidation cycle will be analyzed. Blood samples collected for HMGB1 may be reserved for batch analysis. Refer to the laboratory manual for instructions on collection of a separate sample, versus using blood from the biobanked sample for analysis.
- Biobanked blood and bone marrow may be used to conduct retrospective analyses of biomarkers including, but not limited to, CXCR4, CXCR7, CXCL12, and LSC markers to evaluate their association with observed clinical responses and gain insight into the mechanism of action of dociparstat in AML treatment. Genetic markers known to be related to AML response and or resistance (e.g., clonal selection for TP53 and FLT3 variants) may be examined and additional analyses may be conducted to advance understanding of potential predictors for response (e.g., gene signatures associated with LSCs).

Details on processes for collection, shipment, and destruction of these samples is included in the laboratory manual.

Table 9: Sample Collection Time Points for MRD Analyses and for Biobanking

Sample Time	Analysis	Sample Material
Screening	MRD + Biobanking	10 mL Bone marrow 10 mL Whole blood
Recovery after initial induction (Day ~28-42)	MRD + Biobanking	10 mL Bone marrow 10 mL Whole blood
Recovery after reinduction (Day ~28-42)	MRD + Biobanking	10 mL Bone marrow 10 mL Whole blood
After each consolidation cycle	MRD + Biobanking	10 mL Bone marrow 10 mL Whole blood
Relapse	MRD + Biobanking	10 mL Bone marrow 10 mL Whole blood

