9.5. Interim Analyses

Two interim analyses are planned.

The first interim analysis will be an early unblinded (only to the DMC) assessment of CR, CR with MRD_{neg}, and MRD_{neg}. This analysis will be reviewed by the DMC after 80 evaluable participants complete induction and reinduction (if applicable) assessments. Evaluable participants for this purpose are defined as those who either have a valid MRD result from the induction therapy recovery bone marrow (i.e., Day ~22 to 42), discontinue from induction therapy due to an AE or progressive disease, or die during induction therapy. The study will continue recruitment and enrollment while the interim analyses are being performed; a decision will be made as soon as practicable (targeted within 3 months) after the last participants' last assessments to be included in the analysis.

Three outcomes are possible from this analysis:

- The observed risk difference for CR is >30%, the observed risk difference for MRD_{neg} is >50%, or the combined total of observed risk differences for CR and CR with MRD_{neg} is >40%. The study will remain blinded and continue as planned.
- Observed risk differences for CR, MRD_{neg}, and CR with MRD_{neg} are all <5% The study will be unblinded to all parties and stopped.
- Criteria are not met for either of the preceding scenarios. The study will be unblinded to the sponsor, who, in consultation with the United States Food and Drug Administration, will determine whether to continue or stop the study. If the study continues, participants contributing to the interim assessment will not be used in subsequent inferential analyses and will be replaced. A summary of the data will be shared with investigators and ethics committees and publicly presented. Participants randomized after the interim cutoff and not contributing to the assessment will remain blinded and will contribute to subsequent inferential analyses.

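### Table 1 footnote b provides the MRD assay for CR/CRi participants, while section 8.9, Table 7 and a listed endpoint need it in everyone; the passages should be reconciled, and section 9.5 should say how living non-remitters count

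*Combined protocol and SAP*

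**What the plan says.** The passages on who has an MRD assay after induction do not agree.

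- **Section 1.2, Table 1, footnote b**, which is attached to the MRD row: "For participants who achieve CR/CRi, measurable residual disease assays will be performed by the central laboratory on the recovery marrow sample". It is silent on everyone else.
- **The MRD row itself**, Notes column: "Required. Use first draw of marrow". There is no response condition.
- **Section 8.9**: "For all participants, bone marrow aspirate/biopsy samples will be collected and tested for MRD via MFC at screening and after hematologic recovery".
- **Section 8.2.2, Table 7** defines MRD negativity for every study participant.
- **Section 3** lists as an endpoint "Proportion of participants who achieve MRD_{neg} (regardless of CR), as determined by MFC, at the end of induction and consolidation therapy". MRD negativity combined with CR/CRi is a separate endpoint.

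Three further rules decide what follows from the conflict. Table 7 narrows CRi: "Participants with both residual neutropenia and residual thrombocytopenia are not considered to have achieved CRI". Section 9.4.3 counts missing dichotomous data as failure unless the SAP says otherwise, and places MRD negativity first in the fixed secondary sequence. Section 9.5 counts participants as evaluable for the first interim analysis if they "have a valid MRD result from the induction therapy recovery bone marrow", if they stop induction for an adverse event or progressive disease, or if they die during induction.

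**The concern.** Because CRi needs at least one lineage to recover, a CR/CRi condition on the assay is partly a condition on blood counts. Someone with blasts below 5%, ANC 700/µL and platelets 70,000/µL is not CRi, yet meets CRh and is a responder in the CR/CRh endpoint. Under a restrictive reading of footnote b this person has no MRD result and is scored as not MRD negative, whatever the marrow would have shown.

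Two decisions are exposed. One is the leading test in the secondary sequence. The other is the first interim analysis, where MRD negativity is one of three measures in the continue/stop rule and a valid MRD result is one route into the denominator. If having a result depends on response, the denominator depends on response as well. The rationale in the synopsis and section 2.2 links the drug to platelet recovery, so a difference between arms in who is assayed is conceivable. The documents do not show one.

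**Working it through.** The plan states no figure on this point, so there is none to reproduce. The first step is textual; the others are illustrations. The only rate taken from the plan is the 50% CR in section 9.2. All other rates are assumptions.

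**1. Which participants are affected.** Footnote c and Appendix 7 secure a marrow by Day 42 even without count recovery, so a sample exists. Section 6.1 limits consolidation to participants in CR or CRi, so the conflict bears on induction and reinduction. Under a restrictive footnote b, two groups go unassayed: participants with blasts of 5% or more, and participants with cleared blasts and both cytopenias. The former would be expected to be MRD positive at a 0.1% detection limit, so scoring them as failures changes little. The latter is where MRD results are lost.

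**2. Effect on the MRD endpoint.** Let d be the share with cleared blasts and both cytopenias, and m the MRD-negative share among them, taken as equal in both arms. The recorded MRD-negative rate falls short of the true rate by d × m. The endpoint that disregards CR then equals CR/CRi with MRD negativity, so two listed endpoints become one. With equal true rates, the spurious arm difference is m × (d control − d dociparstat):

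| d control | d dociparstat | m = 0.40 | m = 0.80 |
|---|---|---|---|
| 5% | 5% | 0 points | 0 points |
| 10% | 5% | 0.05 × 0.40 = 2.0 points | 0.05 × 0.80 = 4.0 points |
| 15% | 5% | 0.10 × 0.40 = 4.0 points | 0.10 × 0.80 = 8.0 points |

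If the shares were reversed, the sign would be reversed and a benefit could be hidden.

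**3. Effect on the CR difference at the first interim analysis.** Assume CR 50% versus 65% and CR/CRi 60% versus 75%, so 40% and 25% have neither. Let q be the fraction of these who have no route into the evaluable set, equal in both arms. The CR rates among evaluable participants are 0.50/(1 − 0.40q) and 0.65/(1 − 0.25q):

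| q | Control | Dociparstat | Difference |
|---|---|---|---|
| 0 | 50.0% | 65.0% | 15.0 points |
| 0.25 | 0.50/0.900 = 55.6% | 0.65/0.9375 = 69.3% | 13.8 points |
| 0.50 | 0.50/0.800 = 62.5% | 0.65/0.875 = 74.3% | 11.8 points |
| 0.75 | 0.50/0.700 = 71.4% | 0.65/0.8125 = 80.0% | 8.6 points |

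The difference shrinks even with the same q in both arms, because the arm with more CR failures loses more of them. With equal CR and CRi rates in both arms and the same q, no difference is created.

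**4. Effect on the interim decision.** A simulation of the three-outcome rule used 40 evaluable participants per arm and 200,000 runs. It assumed CR 50% versus 70%, CRi 10% in each arm, and 60% MRD negative among CR/CRi in both arms. With everyone retained, 5% of the remaining participants were taken as MRD negative; otherwise none were.

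| Non-CR/CRi participants retained | Expected CR difference | Continue blinded | Stop |
|---|---|---|---|
| All | 20.0 points | 32% | 3% |
| Half | 15.3 points | 19% | 7% |
| A quarter | 10.9 points | 9% | 12% |

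**The case against.** The best defence is that footnote b never says the assay is confined to CR/CRi participants. A laboratory that tests every recovery marrow, as section 8.9 directs, does not breach it. That is right, and it makes this a conflict of wording rather than a settled design choice. But naming CR/CRi participants does little unless it limits the assay, and the footnote sits on the very schedule row that sites work from.

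A reader might infer that the first interim analysis discards non-remitters as a class. Section 9.5 does not support that: those who die, or who stop induction for an adverse event or progressive disease, stay in. The exposed group is living participants without CR/CRi who are classed as neither. Its size is uncertain because progressive disease is not defined in Table 7 or Appendix 7, and section 7.2 lists failure to reach CR/CRi after reinduction as its own reason for discontinuation.

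A reader might also infer that any arm difference in count recovery carries over in full to the MRD endpoint. It does not. Participants with one lineage unrecovered are CRi and are assayed; only a difference in double cytopenia with cleared blasts matters, scaled by its MRD-negative share. On the available evidence, section 2.2 says only that the drug did not prolong platelet or neutrophil recovery in Phase 2b.

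Finally, sections 9.4.3 and 9.5 leave room for the SAP to treat missing MRD differently, and such detailed rules are not in the document reviewed. That could change the imputation. It could not supply assays that were never run. It is also true that CR with MRD negativity loses no assays under footnote b, although its interim denominator would still change.

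**Conclusion.** Footnote b conflicts with section 8.9, Table 7 and the endpoint that disregards CR. The consequences are conditional on the footnote being applied as a restriction and on the missing-as-failure default. Under those conditions the MRD-negative rate is understated. With a common MRD-negative share, the comparison is biased only if double cytopenia with cleared blasts differs by arm: 2 to 4 points at an assumed 10% versus 5%.

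At the first interim analysis, an assumed true CR difference of 15 points is expected to appear as about 14 to 9 when 25 to 75% of non-remitters are unevaluable. These expected values stay between the 5% and 30% CR thresholds, and stopping requires all three differences to be below 5%. The documents therefore do not support saying that the interim decision would be reversed. What changes is the probability of each outcome, as the simulation shows under its own assumed rates. The point merits correction because it touches a ranked test and a go/stop rule, and because it is easily removed.

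**What to change.** Reword footnote b so that the central laboratory assays MRD on every recovery marrow regardless of response, expressly including the marrow taken by Day 42 when counts have not recovered. That agrees with section 8.9, Table 7, footnote c and Appendix 7. Naming the Day 42 marrow matters because section 8.9 and Table 6 time the sample by hematologic recovery.

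In section 9.5, state that participants who complete induction assessments without CR/CRi are evaluable and count as CR failures even when no valid MRD result exists. Once every recovery marrow is assayed, this sentence mainly covers invalid samples, and it keeps membership of the denominator from depending on response.

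The cost is two wording changes and some additional central assays on marrow that is already collected.
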